#### A.3. Improvement of clinical management of patients with hypertension

A.3.1. Creation of the cardiovascular risk team (CVRT), which will include the head and one leading medical doctor of the hospital unit, and the coordinating doctors of the two health centres. The CVRT will be responsible of supervising good clinical management of hypertension. It will conduct audits of clinical records, periodically selecting a representative sample of clinical records of hypertensive patients and using a structured questionnaire – see annex 5 - to evaluate if the clinical records fulfil the requirements of a complete cardiovascular risk assessment interview and physical examination, doctors' adherence to the hypertension management guideline and some parameters to assess the quality of the provided health care. The CVRT will also provide regular active feedback and support to health professionals involved in the CVRP. It will also supervise the Healthy Hearts service.

A.3.2. Guideline-based standardized diagnostic and treatment protocols: before the start of the intervention, the diagnostic algorithm will be standardized and a simplified and implementable drug treatment algorithm will be defined, based on the national clinical guidelines and in agreement with the general direction of Metrosalud, the direction of the health area and the clinical staff. A core set of antihypertensive medications will be identified and primary and secondary options will be defined for each of the major pharmacologic classes of antihypertensive drugs (diuretics, angiotensin-converting enzyme inhibitors/angiotensin II receptor blockers, calcium channel blockers and Beta-blockers).

A.4. Availability of antihypertensive medications: the availability of the defined core set of antihypertensive medications will be assured through the central store of Metrosalud. Any (un-)availability of antihypertensive medications will be communicated to clinicians at the beginning of each week and *ad hoc* in case of intervening stock-out, in order to timely inform them on possible alternative prescription.

## B. Staff Training

- B.1. Training of clinical staff on good clinical management of hypertension focused on correct BP measurement, use of evidence-based guidelines, cardiovascular risk assessment, use of standardized diagnostic and treatment algorithm, correct prescription of non-pharmacological treatment and anti-hypertensive drugs, patient counselling, and how to tackle clinical inertia. The content, duration, responsible staff and target groups for the training component of the intervention is outlined in annex 1.
- B.2. Training of all health workers involved in hypertension care (doctor, nurses, pharmacists and other non-medical staff) on communication skills and patients' needs assessment. This training will be designed under the "patient-centered medicine" framework (14), aiming at equipping health providers with tools for understanding patients' unique feelings and experience of illness, and to improve their capacity to detect and address social, psychological and behavioural dimensions of hypertension care and control.

## C. Patients and community engagement

- C.1. Patient empowerment: sessions where "expert hypertensive patients" will provide support and peer-education to other patients in need, such as those newly diagnosed or non-adherent to treatment or with uncontrolled hypertension, under the supervision of a social worker.
- C.2. Community engagement: A Community Hypertension Outreach Group (CHOG) will be set up, composed by three voluntary community health workers who will be trained and certified. The CHOG will be created in partnership with the patients' association, which is a very dynamic organization already present in the Commune and interested in engaging in the project. The CHOG will conduct screening activities with measurements of BP in selected public areas of the commune on a weekly rotation basis, for all adults without BP readings in the previous year and referral of those with a positive screening to the nearest health facility for diagnosis confirmation. The CHOG will provide health education with emphasis on healthy lifestyles (tobacco cessation, physical activity and healthy diet). It will contribute to increase community awareness on the importance of hypertension control and on cardiovascular risk detection and prevention. Existing local communication channels such as the community radio and the local newspaper will also be used.

#### 4.2.2 Data Collection

##### 4.2.2.1 Quantitative Data Collection

###### *4.2.2.1.1 Endline population based survey:*

The structured questionnaire “Gaps in hypertension care and control in Medellin, Colombia” (annex 2 to this protocol and Annex 12.1 in protocol “Gaps in hypertension care and control in Medellin, Colombia: cross-sectional survey in two Communes”, Version 2.0, dated 26-AUG-2018,) will be used. The survey questionnaire has been standardized within the Latin American Network for Research on Chronic Diseases for being applied in Colombia, Cuba and Ecuador and has also been validated for each country.

Participants will be interviewed on their socio-demographic characteristics, health seeking behaviour, risk factors (e.g. smoking, alcohol abuse, physical inactivity) and previous and current health problems (e.g. diabetes, dyslipidaemia). Those referring previous diagnosis of hypertension will be asked on their treatment, follow-up, anti-hypertensive pharmacological and non-pharmacological treatment and compliance with the treatment.

###### *4.2.2.1.2. Data collection at health services:*

**Data sources:** databases of the Subsidized Regimen and of the non-insured poor population, electronic clinical and billing records of Metrosalud, registers of the “Healthy Hearts” service (Annex 3, 4 and 5), exit-interview forms (Annex 6), audit form (Annex 7, an adapted format for the audit of clinical records in use at Metrosalud), lists of participants and minutes of meetings and training activities, test results during trainings, registers and inventory at the pharmacy service, and report of activities by health professionals.

Besides the data explicitly mentioned in the annexes and tables of this protocol, we will collect the data mentioned below.

**Data extracted from the databases of the Subsidized Regimen and of the non-insured poor population (data will be extracted either in the intervention and in the control commune):**

- the total adult population (by sex, age, place of living and health insurance affiliation) for whom Metrosalud is responsible in the catchment area (target population).

**Data extracted from the billing and electronic clinical records of Metrosalud (data will be extracted either in the intervention and in the control commune):**

- number of patients enrolled in the CVRP.
- regarding patients enrolled in the CVRP: sex, age, frequency and results of cardiovascular risk assessment, prescribed pharmacological/non-pharmacological treatment, BP figures, major comorbidities and complications.
- number of patients who have missed a hypertension-related appointment

**4.2.3 Qualitative component** The qualitative component will be carried out by a social scientist with previous experience in the use of qualitative methods, under the supervision of a senior sociologist from the Latin American Network for Multidisciplinary Research on Chronic Diseases with expertise in implementation fidelity.

We will collect data concerning the implementation process and its fidelity, following the modified version of the Conceptual Framework for Implementation Fidelity (18; 19). This framework defines fidelity as a measurement of adherence, with its subcategories: content, frequency, duration, and coverage (dose). It identifies six moderating factors: comprehensiveness of intervention description, strategies to facilitate implementation, quality of delivery, recruitment, participant responsiveness, and context (20). The nature of adaptations that are likely to occur during implementation and their implication for fidelity should be also analysed prospectively for each intervention (21).

Our fidelity assessment will focus on all intervention components. Data collection methods will include non-participant observations, key informant interviews and document analysis. To measure the subcategories of adherence, specific forms will be created for self-registration for each component of the intervention. All actors responsible with the implementation will be trained in self-registration of all the activities. Self-registration forms will be collected monthly.

This information will be used to monitor the process and identify those activities and relevant actors that will be subject of interviews and non-participant observations. The observation will have the purpose to triangulate self-registration information by providing real-time information on whether actual implementation is done according to the plan. Observations will be accompanied by semi-structured interviews to clarify the observed practices, moderating factors, adaptations introduced by the different stakeholders and possible explanations for adaptations. Observation and semi-structured interviews will be systematically applied to a purposive heterogeneous sample of

implementation units and actors. While exploring moderating factors, a specific section will be added to the semi-structured interview guide to explore socio-economic evolutions, health system & service changes and other activities and events that might bear on the outcomes. Similar aspects will be explored also in the control area.

The overall experience of patients with the implementation of the intervention will be explored through in-depth interviews, carried out at different phases of implementation. The estimated sample size for the interviews will be 25 – 30 for each phase. Data saturation will be taken into consideration. The qualitative data collection will fit the overall process evaluation plan.

### 4.3 Data Analysis

#### 4.3.1 Quantitative Data Analysis

The main outcomes (dependent variables) of the analysis at population level will be the gaps in hypertension care and control (Table 1). Uni, bi- and multivariate analysis will be performed. For the main outcomes, difference in difference measures will be calculated (endline-baseline changes in the intervention minus endline-baseline changes in the control commune). Where relevant, we will stratify on affiliation to Subsidized or Contributory insurance schemes. Logistic regression models adjusting for potential confounding variables will be fitted. Unadjusted and adjusted Odds Ratios (ORs) and their 95%CI will be calculated.

The indicators for monitoring the implementation and measuring the results and effects of the intervention at health service level are listed in the following table (Table 3). They have been elaborated also taking into account the standardized performance indicators proposed by the SHTP and Global Hearts project (2). The indicators will be measured both in the intervention and in the control area, at baseline, at regular intervals during implementation, and at endline.

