## **4.2 Procedures**

A multi-component intervention, detailed below, will be implemented in the intervention area, while standard hypertension care will be provided in the control area.

Each intervention component will be standardized and described in a field manual for the improvement of hypertension management. For each component we will clearly define: subcomponents or activities specifying implementation level and units, responsible, target population, content, methodology and way of delivery, time, duration, key improvement factors, functioning principles and expected results per activity.

A logic model of the intervention will be elaborated to provide a graphical depiction of the inputs, processes, immediate, short-term, and long-term outcomes, and the relationship and sequence between the different intervention components and critical points in the implementation process as a whole. Critical points are stages or activities in the process, susceptible to be measured, in the

absence of which other stages or activities cannot be implemented. The intervention activities will be implemented by Metrosalud staff of the health structures in the Commune with technical assistance from the investigation team.

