##### **A. Health services organization**

A.1. Hypertension screening: 1) all adults aged 35 years or older presenting to any health service (including clinical and support services) will be asked if they had their BP measured in the previous year. If not, they will be referred to a specific nursing hypertension service (“Healthy Hearts” service, see A.2 below) for a BP measurement, using a ticket stub for referral. 2) Doctors and nurses encountering presumptive hypertensive patients (individuals not reporting a previous diagnosis of hypertension but presenting BP higher than 140/90), will refer them to the “Healthy Hearts” service for confirmation of the diagnosis with serial BP measurement. 3) The entire health care flow for patients with a high BP measurement within health facilities will be standardized in order to guarantee continuity of care and correct diagnosis.

A.2. “Healthy Hearts” service: an auxiliary nursing station with extended opening hours and providing services such as BP measurement, global cardiovascular risk assessment and preventive counselling. It oversees serial self-measured BP monitoring within the health facility premises to exclude white coat hypertension, providing devices and patient education on self BP measurement. It will ensure retention and follow-up of all people with a high BP measurement at screening (at service level or in the community - see C.2 below) in order to guarantee that final diagnosis (hypertensive or not) is reached. It will refer to clinicians of the CVRP all newly diagnosed hypertensive patients. Through phone calls and/or SMS to patients and linkage with community agents, it will promote effective referral and manage non-attendance to follow-up CVRP consultations. It will administer periodical anonymous exit-questionnaires (annex 6) to hypertensive patients exiting from CVRP

consultations in order to assess effective BP measurement and the quality of pharmacological and non-pharmacological advice during medical consultations. Results will be transmitted to the cardiovascular risk team (see A.3.1 below).

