6. High calculated cardiovascular risk	Hypertensive patients with calculated cardiovascular disease risk $\geq 20\%$ in 10 years and systolic blood pressure (BP) $\geq 140/90$ mm Hg at last BP measurement during the last year.	Number of hypertensive patients enrolled in the CVRP	Billing and electronic clinical records	Pharmacological treatment (yes, no), sex, age	Biannual
7. Prevalence of controlled	Hypertensive patients with documented	Number of hypertensive patients	Billing and electronic clinical	Pharmacological treatment (yes,	Biannual

hypertension	systolic BP <140 mm Hg and diastolic BP <90 mm Hg in at the most recent BP measurement during the last year.	enrolled in the CVRP	records	no), sex, age	
8. Prevalence of controlled hypertension 6 months after enrolment in the CVRP	Hypertensive patients who started treatment 6 months before the reporting trimester and have systolic BP <140 mm Hg and diastolic BP <90 mm Hg at follow-up visit during the reporting trimester	Number of hypertensive patients enrolled in the CVRP who started treatment 6 months before the reporting trimester	Electronic clinical records	Sex, age, pharmacological treatment (yes, no), non-pharmacological treatment (yes, no)	Quarterly
9. Uncontrolled hypertension in patients with cardiovascular disease, renal disease or diabetes	Hypertensive patients diagnosed $\geq 6$ months before the start of the reporting period, and cardiovascular disease, renal disease, or diabetes mellitus, who had systolic BP $\geq 140$ mm Hg or diastolic BP $\geq 90$ mm Hg at the most recent BP measurement during the last	Number of hypertensive patients enrolled in the CVRP $\geq 6$ months before the start of the reporting period	Electronic clinical records	Pharmacological treatment (yes, no), sex, age	Quarterly

	year				
10. Uncontrolled hypertension 2	Hypertensive patients diagnosed $\geq 6$ months before the start of the reporting period who had systolic BP $\geq 160$ mm Hg or diastolic BP $\geq 100$ mm Hg at the most recent BP measurement during the last year	Number of hypertensive patients enrolled in the CVRP $\geq 6$ months before the start of the reporting period	Electronic clinical records	Pharmacological treatment (yes, no), sex, age	Quarterly

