**C. Indicators related with the clinical training of health care staff for improvement of hypertension care**

Indicator	Numerator	Denominator	Data Source	Breakdown	Frequency of collection
32. Realized trainings	Number of realized training sessions for health care staff	Number of programmed training sessions for health care staff	Training plan List of attendance	Type of training	Annual
33. Trained health care professionals	Number of trained professionals	Total number of professionals	Training plan List of attendance	Type of health professional Type of training Health facility	Annual

34. Effectiveness of training in improving clinical knowledge	Average post-test score minus average pre-test score	NA	Pre- and post-test	Type of health professional Training session Health facility	Once
35. Effectiveness of training on acquiring BP measurement skills	Number of trained professional passing post-training practical test	Total number of trained professionals undergoing post-training practical test	Post-training practical test for certification on BP measurement following international standards	Type of health professional Health facility	

**D. Indicators related with the management of the pharmacy service to guarantee the availability of the essential anti-hypertensive medication**

Indicator	Numerator	Denominator	Data Source	Breakdown	Frequency of collection
36. Notification on availability of core set of anti-hypertensive drugs	Total number of notifications made in a month	Number of weeks in the respective month	Register of notification at the pharmacy service	Type of health facility	Monthly
37. Number of weeks without availability of essential antihypertensive drugs	Number of weeks without availability of one or more essential antihypertensive drugs	NA	Pharmacy inventory	Type of health facility Name of the antihypertensive	

**E. Indicators related with patients and community engagement for improving hypertension care and the prevention of cardiovascular diseases**

Indicator	Numerator	Denominator	Data Source	Breakdown	Frequency of collection

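### BP measurement is retrained and certified in the intervention commune only, so BP-based Table 3 indicators 6 to 12 should not carry conclusions about the intervention's effect on BP control

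*Combined protocol and SAP*

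**What the plan says.** Three parts of the protocol bear on this.

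**Measurement changes in the intervention commune.** Component B.1 in section 4.2.1 provides "Training of clinical staff on good clinical management of hypertension focused on correct BP measurement". Indicator 35 in Table 4, part C, checks that skill; its data source is a "Post-training practical test for certification on BP measurement following international standards". Component A.2 also creates a nursing station: "It oversees serial self-measured BP monitoring within the health facility premises to exclude white coat hypertension".

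**It is not described for the control commune.** Section 4.2 puts the intervention in one area, "while standard hypertension care will be provided in the control area". No BP training, device standard or check of recorded BP is described for control clinics.

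**Clinic-recorded BP has an effect role.** Section 4.3.1 says of Table 3: "The indicators for monitoring the implementation and measuring the results and effects of the intervention at health service level are listed in the following table". It adds: "The indicators will be measured both in the intervention and in the control area, at baseline, at regular intervals during implementation, and at endline". Indicators 6 to 12 come from electronic clinical records, with billing records also named for 6 and 7. Indicator 7, for example, counts patients with "systolic BP <140 mm Hg and diastolic BP <90 mm Hg in at the most recent BP measurement during the last year". Indicators 6, 9, 10 and 11 also use the last or most recent reading of the year. Indicators 8 and 12 use the reading at a follow-up or clinical visit.

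**The concern.** The staff whose technique is changed by the intervention also produce the readings that define indicators 6 to 12. The change begins after baseline and in one commune. Subtracting baseline values removes a constant difference in technique between communes, but not a difference that starts with the intervention.

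Table 3 is the facility-level evidence for the secondary objective of better hypertension care in the public services of Santa Cruz. If recorded BP falls there because patients are measured more correctly, indicator 7 improves with no change in true BP. If better technique ends favourable rounding just below a threshold, indicator 7 can worsen while true control improves. The documents do not allow the direction to be predicted. Section 8.1 limits the record extract to aggregate data, so the two explanations would be hard to separate afterwards.

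**Working it through.** The plan gives no figure for this point. Its only sample size, 280 hypertensive individuals for a 10-point difference (section 4.1.2), concerns the survey control gap and not Table 3. So the first step is to compare the text, and the second is an illustration of size.

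**Step 1. The two sources of BP.**

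| | Survey BP (main outcomes) | Clinic-recorded BP (indicators 6 to 12) |
|---|---|---|
| Who measures | Surveyors trained in BP measuring (section 6) | Routine clinical staff |
| Same procedure in both communes | Yes; baseline methodology repeated (4.1.2) | Retraining and certification in Santa Cruz only |
| Stated role | Main outcomes, by difference in difference (4.3.1) | Monitoring, and results and effects at health service level (4.3.1) |

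Only the right-hand column has a measuring procedure that the intervention itself alters.

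**Step 2. How far a measurement shift could move a share.**

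Input from the documents: 41% of aware hypertensives uncontrolled in the 2016 survey (section 1.2), so 59% controlled.

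Assumptions not in the documents: systolic BP alone, normally distributed; SD 16 to 20 mmHg; a constant change of *d* mmHg in recorded BP.

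Formulas, with *d* positive when recorded BP falls and k = Φ⁻¹(0.59) = 0.2275:

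- change in share below 140 = Φ(k + d/SD) − 0.59
- share above 160 before any shift = 1 − Φ(k + 20/SD). With SD 16 this is 1 − Φ(1.4775) = 7.0%; with SD 20 it is 1 − Φ(1.2275) = 11.0%
- change in share above 160 = Φ(k + 20/SD) − Φ(k + 20/SD + d/SD)

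Example, SD 16 and d = 2: Φ(0.2275 + 0.125) − 0.59 = +4.8 points.

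| SD | Recorded BP | Share below 140, change in points | Share above 160, change in points |
|---|---|---|---|
| 16 | falls 2 | +4.8 | −1.5 |
| 16 | rises 2 | −4.9 | +1.8 |
| 20 | falls 2 | +3.8 | −1.8 |
| 20 | rises 2 | −3.9 | +2.0 |
| 16 | falls 5 | +11.5 | −3.3 |
| 16 | rises 5 | −12.4 | +5.2 |
| 20 | falls 5 | +9.4 | −4.0 |
| 20 | rises 5 | −9.9 | +5.4 |

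The 140 column fits indicator 7 best. The 160 column is nearer to indicators 10 and 11, which use 160/100. Indicators 6, 9 and 11 add further conditions (high risk, comorbidity, three or more drugs) over a denominator of all enrolled patients. Their base shares are smaller and these figures do not carry over to them.

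The 59% is only an anchor. The survey definition of control allows 150/90 from age 60 (section 4.1.4), while Table 3 uses 140/90 at all ages.

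**The case against.** The strongest reply is that the comparison is never prescribed. Section 4.3.1 reserves the difference-in-difference for the main outcomes, which are the survey gaps of Table 1. Table 3 is titled as performance indicators and has no contrast, test or model between communes. This stands, and it limits the point to interpretation. It does not remove the point: the text assigns the indicators to effects as well as monitoring and collects them in both areas before and after, which invites exactly that reading.

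A reader might infer that the Healthy Hearts serial and self-measured readings feed indicators 6 to 12. The documents do not show this. Those readings serve to confirm diagnosis, and the results in indicators 17 to 20 come from that service's own registers. Indicators 8 and 12 already name a visit reading. Indicator 16 does list clinical records among its sources, and wording such as "at the most recent BP measurement during the last year" does not exclude such a reading, so leakage is possible but not established. Even if records held the mean of three readings, the effect of averaging alone on the uncontrolled share would be about 0.3 to 1.7 points (assumed total SD 18 and within-person SD 6 to 12 mmHg).

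A reader might also infer that audited staff would record favourable values. Nothing in the documents rewards staff for the BP they write down. Section 5 makes exit interviews anonymous, keeps the resulting feedback collective, and rules out using those results to evaluate individual staff.

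That better technique is a legitimate part of the intervention is true. A more accurate reading is still not the same as better-controlled BP, which is what these indicators are named for.

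**Conclusion.** The point holds as a limit on interpretation. Retraining and certification change the reading behind indicators 6 to 12 in one commune after baseline, and the plan gives those indicators an effect role without any caution.

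It would be tempting to conclude that the trial's main result is biased. The documents do not support that: the control gap and the other Table 1 gaps come from the survey and do not depend on clinic-recorded BP.

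The size is conditional. With the stated model, a 2 mmHg shift gives about 4 to 5 points at the 140 cut and about 1.5 to 2 points above 160. A 5 mmHg shift gives about 9 to 12 and 3.3 to 5.4 points. Neither shift has a basis in the documents, so these figures show sensitivity and do not estimate a bias. The 10-point survey target is not a benchmark for Table 3. This is an inexpensive improvement to the plan and not a threat to its main analysis.

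**What to change.** In section 4.3.1, next to the sentence that introduces Table 3:

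- keep collecting indicators 6 to 12 in both communes, for monitoring and context;
- state that any conclusion about the intervention's effect on BP control rests on the survey BP;
- state that changes in indicators 6 to 12, whether compared between communes or read before and after within Santa Cruz, may partly reflect changed BP measurement.

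Optionally, for the indicators that use the last or most recent BP (6, 7, 9, 10 and 11), count only readings taken at Cardiovascular Risk Program consultations in both communes. This aligns the type of reading. It does not remove the retraining effect, so it cannot replace the wording above.

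The main change costs a few lines of protocol text and no new data; the optional one needs a tighter definition in Table 3 and in the record query. The real cost is that the sponsor gives up a facility-level claim of effect on BP control.
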